12.3 Ongoing management of participants

Treatment as usual

GPs may arrange to review participants allocated to TAU at ongoing appointments as required.

Intervention arm

The case manager for participants in the intervention arm will usually be the CAB advisor (in a small minority of cases this may be the GP or nurse). Participant contact will be maintained through telephone, e-mail, text, face-to-face review or a combination of these methods. Contacts will be recorded by CAB advisors on the password protected study database.

On-going pathways of care will include progress reviews by the GP and the CAB advisor. Optional pathways will include a) referral on to more intensive CAB debt counselling services, b) to other social inclusion services based on assessment of problems within comprehensive assessment and c) referral on to IAPT services for psychological therapy.

13 PARTICIPANT FOLLOW-UP

Following the baseline visit, all participants will undertake two further assessment visits with a researcher - one four months post baseline visit and one 12 months post baseline visit. The researcher will arrange the dates for the four and 12 month follow up visits at the end of the baseline assessment and in addition will send a letter confirming the agreed dates to the participant. Participants will receive reminders of visit dates/times for follow up visits from the local research team no earlier than one week before the planned visit, to reduce risk of losses to follow up. Reminders will be sent out by text, telephone, e-mail or post (as preferred by participant). Researchers will arrange to meet participants in the participants' own homes or at alternative

venues (GP practice, local community premises or University sites) as appropriate and convenient in each case. Participants will receive reasonable travel expenses and a £10 shopping voucher for each completed data collection visit to defray their expenses and time. In the event that a face to face follow-up visit cannot be arranged, telephone, postal or on-line data collection options will be offered. Where participants fail to attend pre-arranged follow up meetings reasonable attempts will be made to contact participants to confirm if they wish to re-arrange the visit. Should participants not wish to arrange further follow up, they will be asked if they would be willing to complete the single primary outcome questionnaire (BDI-II) by telephone. Should participants prefer not to complete the primary outcome measure no further attempts to contact the participant will be made. Participants indicating that they do not wish to complete any further follow up will be asked if they would be happy to provide a reason (to help inform future research development), but will also be advised that they are under no obligation to do so.

14 TRAINING

The lead study GP in each participating practice and his/her nominated deputy will be trained before starting recruitment in the trial design, assessment protocol and NICE guided 'treatment as usual' pathways. The local manager will visit to support recruitment, check fidelity to protocol and answer queries. This is likely to be monthly initially and then every 6-8 weeks once the study is established.

Researchers conducting qualitative interviews (see section 16.2) will receive training from experienced CAB staff who work in the field of debt and mental health and from service user advisors. Specific training and supervision will be provided by senior academics to ensure researchers develop the relevant skills to conduct interviews effectively: both from an ethical and scientific standpoint. Participants may be particularly concerned about issues such as confidentiality and how their data are reported and handled and assurances will be given at the interview, alongside the information sheet and the consent process. All aspects of the interviews and topic guides will reflect these sensitivities.

15 SAFETY

Participants will be advised at the start of the baseline interview that if their answers indicate that they are currently at risk of serious harm to their health, or that their life may be at risk, the researcher will advise them to see their GP as a matter of urgency, and will inform the study GP that the participant has been given this advice.

Researchers will contact the study GP or the on-call GP if they have specific concerns about the participant's welfare and current risk, in particular, if participants indicate they are suicidal during data collection visits – either verbally or as indicated on the BDI-II. Participants who indicate that they are actively suicidal will be encouraged to contact the study GP promptly, and the researcher will explain that the study GP or the on-call GP will be informed of the researcher's concerns about their welfare and current risk – with or without participant's permission. The visit will be brought to a close at this point and it will be explained to the participant that should they wish to continue participation in the study they will be able to do so once they have discussed current risk with the participating GP or on-call GP. In this case, the RA will explain that they will contact the GP in approximately two weeks to check if it would be appropriate to re-contact the participant. The purpose of the RA re-contacting the GP is to ensure that further participation in the study has been assessed as appropriate by a clinical expert.

If a participant circles either statement 2 or 3 on item nine of the BDI II the participant will also be considered to be at significant risk. In such circumstances the researcher will inform the relevant participating GP or the on-call GP at the participant's GP practice and the assessment visit will be terminated as detailed above.

Researchers will receive training about assessment of risk from their local principal investigator (all senior clinicians) and will also be given a direct contact number for a senior mental health expert who can be contacted to discuss individual cases as and when necessary. The Principal Investigators will also liaise with the participating GPs as required. CAB advisors will follow CAB protocol and guidance regarding client risk and breaching confidentiality.

Researchers conducting assessment visits/qualitative interviews will follow a lone working protocol.

15.1 Adverse event reporting

There is no requirement to report non-serious adverse events in this study.

For the purposes of this study, any event that falls into one of the following categories, or is a significant medical event in the opinion of the principal investigator, should be reported to PenCTU as a serious adverse event (SAE) as soon as possible after the event comes to light, regardless of whether the event is considered to be related to any of the trial interventions:

- Death
- Immediately life threatening illness
- Hospitalisation or prolongation of hospitalisation
- Results in persistent or significant disability or incapacity

GPs and researchers will be required to report any such event on a study-specific SAE form to PenCTU by fax within 48 hours of becoming aware of the event where possible. All SAEs will be reported onwards by PenCTU to the local PI, the CI and trial manager. The CI will report all SAEs to the study sponsor, the trial management group and the Trial Steering Committee. Any SAE considered by either the PI or the CI to be related to the administration of the trial procedures and unexpected will be notified to the REC. Expected SAEs would include hospitalisation for self-harm/attempted suicide and depression.

16 DATA COLLECTION

16.1 Data collection measures and timepoints

Participants will undertake three assessment visits with a researcher - at baseline, four and 12 months following the baseline visit. Follow up visits will take place at these timepoints regardless of the timing of the initial CAB assessment appointment. In addition to the assessment visits a purposive sample of participants will be invited to take part in two qualitative interviews (see section 16.2).

The data collection schedule for the internal pilot trial is shown in Table 1. The data collection schedule may be reduced for the main trial dependent on feasibility/acceptability of measures – determined during internal pilot trial.

Table 1: Data collection schedule

	Baseline	4 month	1 year
Demographic (Age, sex, deprivation score etc.)	✓		
BDI II	✓	✓	✓
Alcohol AUDIT & Substance Misuse Screen (DAST)	✓	✓	✓
BAI	✓	✓	✓
Short WEMWEBS	✓	✓	✓
CSRI (adapted for trial)	✓	✓	✓
EQ5D	✓	✓	✓
MANSA	✓	✓	✓
Stanford Presenteeism Scale	✓	✓	✓
CAB/Control debt assessment & outcomes Q	✓	✓	✓
GSQ		✓	
Hope Trait Scale	✓	✓	
LED-S	✓	✓	
OAS, RSQ	✓	✓	
Qualitative Interviews			
Participant Purposive Sample	✓	✓	
Professional (GP/CAB staff) purposive sample			(6-12 months)

16.2 Qualitative data collection

Internal Pilot Trial

Approximately 30-45 participants (10-15 at each site) purposively sampled for age, sex, geography, priority or non-priority debt and severity of depression will each undergo two interviews with a qualitative researcher. Participants who indicated on the baseline consent form that they would be happy to be contacted about taking part in qualitative interviews will be identified by research teams at each site and cross referenced with above variables on PenCTU database to identify a purposive sample of individuals for qualitative interviews.

The first interview will take place approximately 2-4 weeks after the baseline assessment visit and the second interview approximately four months later. The researchers conducting the qualitative interviews at each site will be different from the researchers undertaking assessment visits at each site in order to preserve blinding of assessors. It is anticipated that these interviews will take place face to face and in a setting convenient for the participant, but if this cannot be organised, telephone interviews will be conducted, subject to participant consent. Interviews will be audio-recorded with participant consent and anonymised during transcription. A separate written consent form will be completed prior to the start of each qualitative interview. Transcripts will be identified by participant trial number and each will also be given a pseudonym.

The qualitative interview topic guides will be developed in conjunction with Service User advisors and will be adapted following initial analysis. The baseline narrative interview will explore participant's biographies of depression, anxiety and debt, the impact on participant's life (families, friends, work and other activities) and perceptions of practical aspects of debt (dealing with bailiffs, creditors, debt collectors and associated emotions e.g. fear). The follow-up semi-structured

interview four months later will enquire about developments since entering the trial, exploring the role of psychological, social and economic factors involved in recovery (or not) from debt and depression, including changes in employment, relationships with families, friends, and the connections with debt. The follow up interview will also check for evidence of contamination amongst controls (increased focus on debt in GP consultations, recommendation to attend or referrals for debt advice) and their experience of care and interventions (to check GPs concordance with trial protocols).

Anonymised electronic copies of transcripts will be stored on approved University computers at each site, which are password protected and virus checked. Data will only be stored on the University's managed network server and not on the computer's own hard drive. Any paper copies of participant transcripts will be stored separately to identifiable information (e.g. consent forms) and will be held in locked filing cabinets. Original audio files will be destroyed after four months – once transcripts have been checked for meaning or missing words. The qualitative researchers will keep field notes which will be stored and used according to standard confidentiality protocols.

Main trial

A further 30-45 interviews will be conducted in the main trial, with participants purposively sampled as above and concentrating on new sites (e.g. rural) in particular.

16.3 GP and CAB staff interviews

A process evaluation will be undertaken using semi-structured interviews with GPs and CAB staff participating in the study (10-15 of each). These findings will be triangulated with relevant CSRI data on appointments, process records from CAB visits and completed comprehensive assessments – which will be developed in consultation with GPs and CAB in the initial set up phase. GP and CAB staff interviews will be done once the participating practices have been involved in the trial for at least six months and will commence during the pilot trial. The purposive sampling frame will depend on whether the full trial is modified to a cluster design, but will seek to cover a range of sites and invite GP and CAB staff for interview after they've been participating for 6 – 12 months.

17 SUBJECT COMPLETION/WITHDRAWAL

The expected duration of participant involvement in the study is one year, with participants normally completing the study after the 12 month follow-up assessment. The trial itself will end on the date that the last participant undergoes his/her last study assessment. Participants who withdraw from the intervention and/or follow-up will not be replaced within the study. Data collected prior to withdrawal will be included in the study analysis unless a participant specifically requests that their data are removed from the database.

17.1 Withdrawal from intervention/discontinuation of follow-up

A participant may withdraw from the trial at any time, without being required to give a reason and without his/her care being affected.

The trial analysis is based on intention to treat, so all participants will be encouraged to continue with follow-up as per protocol even if, post-randomisation, they fail to attend any appointments with the GP or CAB advisor or the trial intervention is only partially completed. Participants who attend the assessment appointment with the GP but then refuse CAB contact or fail to have any contact with a CAB advisor following referral to CAB by GP, will be considered to have partially completed the intervention. Participants who refuse CAB referral and also indicate that they do not wish to complete follow-up visits with the researcher, will be withdrawn from the study at this point. Control

participants will be treated as this even if they attend CAB or debt advice through other means, and whether or not they attend the GP appointment for assessment and leaflets on debt.

Participants will also be withdrawn from the trial if they indicate during assessment/qualitative/CAB appointments that on-going participation would be likely to result in serious risk of harm to the participant themselves or to members of the study team or CAB service.

Withdrawal from trial follow-up, and the reason, if known, should be clearly documented in the participant's research/clinical records and the appropriate documentation should be completed and returned to the CTU as soon as possible as official notification of the withdrawal. Participants should be asked to explain their reason for withdrawing, but are under no obligation to do so.

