12.2 Intervention arm

Participants in the intervention arm will undergo a shared comprehensive assessment, starting with an initial GP review which mirrors that of the control group. At that visit, the GP will advise the participant of the intention to refer the participant to a CAB advisor and the GP will confirm that the participant is happy for this to be done. The GP will complete an electronic referral form that will include a statement that confirms the participant's agreement to be contacted by a CAB advisor and their consent to sharing of specified information between the CAB and GP, for the purposes of the shared comprehensive assessment. Participant's written, signed agreement to sharing of contact details and specific information for the purpose of the shared comprehensive assessment between GP and CAB will be retained by the GP practice. All participants will receive the study-specific debt advice leaflet and the RCPsych debt advice leaflet. Participants who do not wish to be contacted by a CAB advisor will be followed up as planned (see section 13), if they are still willing to do so. The GP will inform the study team via the web-based database that the participant has declined CAB intervention.

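### Section 17.1 withdraws intervention participants who refuse both CAB referral and visits without the telephone BDI-II request of section 13, adding an arm-specific route to missing primary outcome data

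*Protocol*

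**What the plan says.** Four parts of the protocol bear on this.

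- **Section 12.2 (Intervention arm).** At the first GP review "the GP will advise the participant of the intention to refer the participant to a CAB advisor". On refusal: "Participants who do not wish to be contacted by a CAB advisor will be followed up as planned", under section 13 and provided they are still willing. The control-arm pathway in section 12.1 contains no CAB referral.
- **Section 13 (Participant follow-up).** "In the event that a face to face follow-up visit cannot be arranged, telephone, postal or on-line data collection options will be offered". For those who do not want to arrange more follow-up, "they will be asked if they would be willing to complete the single primary outcome questionnaire (BDI-II) by telephone". Attempts at contact stop if they decline that too. No arm is excepted.
- **Section 17.1, opening of the second paragraph.** "The trial analysis is based on intention to treat, so all participants will be encouraged to continue with follow-up as per protocol", including people who attend no GP or CAB appointment.
- **Section 17.1, later in the same paragraph.** Those who turn down referral to CAB "and also indicate that they do not wish to complete follow-up visits with the researcher, will be withdrawn from the study at this point". There is no reference to section 13 and no mention of the telephone BDI-II. The next sentence keeps controls in their arm whether or not they attend the GP appointment or find debt advice elsewhere.

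**The concern.** The section 17.1 trigger is unwillingness to have visits, not unwillingness to have any contact. Section 13 treats these as different things: it puts a single telephone questionnaire between declining visits and the end of contact. Section 17.1 goes directly from the first to the last for one group, and only intervention participants can belong to it.

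The refusal can come very early. The first GP appointment is due within a week of randomisation (section 12.1, which the intervention-arm review mirrors), and the first outcome assessment is at 4 months. Someone withdrawn at that appointment has a baseline BDI and nothing afterwards, and section 17 does not replace withdrawn participants.

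At stake is the comparability of the arms at 12 months. If primary outcomes that could have been obtained are lost because of a reaction to the offered intervention, the people analysed in the two arms are no longer selected in the same way.

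**Working it through.** **1. Is the trigger arm-specific?** CAB referral by the GP exists only in section 12.2, so a control cannot refuse it. A control who loses interest after randomisation stays enrolled and can reach the section 13 steps at 4 and 12 months. An intervention participant who refuses referral and visits at the GP appointment is, as written, already out of the study by then. The extra route is one-sided.

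**2. Do the sections agree?** Section 13 asks for the telephone BDI-II before contact ends. Section 17.1 withdraws without asking, although its own paragraph says that everyone is encouraged to continue. Sites could follow either text.

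**3. The plan's own figures.** Section 21.1 gives a target difference of 3.5 BDI, SD 9, two-sided 5% alpha, 90% power and 135 per arm. The normal approximation gives n = 2 × (1.960 + 1.282)² × 9² / 3.5² ≈ 139; 135 per arm gives power 0.892. That is close enough to take 3.5 as the yardstick. With 195 per arm and 20% attrition, 195 × 0.8 = 156 per arm are analysed.

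**4. Size of the possible bias.** The protocol gives none of the three inputs below, so all are assumptions.

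Bias in the intervention mean = p × a × d, where
- p = fraction of the intervention arm meeting the rule (assumed 5-10%; of 195, 9.75 to 19.5, so about 10 to 20 people);
- a = share of these who would have accepted a telephone BDI-II (assumed 50-100%);
- d = difference in 12-month BDI between those lost and those retained (assumed 5 points).

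| p | a | d | p × a × d | as % of 3.5 |
|---|---|---|---|---|
| 0.05 | 0.5 | 5 | 0.125 | 3.6% |
| 0.05 | 1.0 | 5 | 0.25 | 7.1% |
| 0.10 | 0.5 | 5 | 0.25 | 7.1% |
| 0.10 | 1.0 | 5 | 0.50 | 14.3% |

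Here p is a fraction of those otherwise analysed. If p is instead a fraction of all 195 randomised and the loss comes on top of the 20% attrition, divide by 0.8: the ends become 0.125 / 0.8 = 0.156 and 0.50 / 0.8 = 0.625 BDI (4.5% and 17.9% of 3.5).

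**5. Wider range.** On the second basis with a = 1, p from 2% to 10% and d from 2 to 9 points, the bias runs from (0.02 / 0.8) × 2 = 0.05 to (0.10 / 0.8) × 9 = 1.125 BDI, or 1% to 32% of the target. These are upper bounds for each p and d, because they suppose that everyone would have taken the call. The fractions, and so the biases, are the same for the cluster design with 235 per arm.

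**6. Power.** Ignoring any design effect, power with 156 analysed per arm is 0.930. Losing a further 2%, 5% or 10% of the 195 from the intervention arm gives 0.927, 0.922 or 0.913. The issue is bias, not sample size.

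**The case against.** The best defence is that section 17.1 never says the telephone BDI-II is withheld. Section 13 excepts no arm, and section 12.2 sends CAB refusers to section 13 if they are still willing. A reader might infer that the protocol deliberately removes the fallback from this group; it does not say so. What stands is a contradiction between two sections, and on its natural reading section 17.1 ends participation before the later step can be reached.

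Secondly, the telephone request in section 13 follows a sentence on missed appointments, and people who want no follow-up at all are simply asked for a reason. A control who declines everything early could be handled that way too. This narrows the asymmetry, but section 17.1 still supplies an explicit trigger for immediate withdrawal that only one arm can meet.

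A reader might also infer that primary outcome data go missing in the intervention arm only. The protocol does not support that: anyone may withdraw at any time, contact ends for anyone who declines the BDI-II, and the 20% attrition allowance is not split by arm.

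The group may also be small. Both refusals are required, participants identify themselves as worried about debt, and the section 4 summary (though not the list in section 10.2) excludes people who do not want debt support through the practice. This is fair, and it limits the likely size.

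Finally, section 21.2 adjusts for baseline score and plans sensitivity analyses for missing data, whose detail may properly sit in the statistical analysis plan. These mitigate the problem. They cannot replace an outcome that a telephone call would have obtained, and they rest on assumptions about people with no post-randomisation data.

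**Conclusion.** The concern holds in a limited form. Sections 13 and 17.1 conflict, and section 17.1 followed as written adds a route to missing primary outcome data that is open in the intervention arm only, depends on reaction to the intervention, and runs against the protocol's own intention-to-treat statement.

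The size is unknown. The 0.13-0.5 BDI range (4-14% of the 3.5 target) rests on assumed values for the refusal rate, acceptance of the call and the BDI gap; d should be read as the gap left after adjustment for baseline.

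The direction is also open. A reader might infer that the intervention would look too good because refusers do worse. But someone whose mood or debt worry has eased might refuse as well, and the bias would then run the other way. Nothing in the protocol settles this. The point is a cheap protection against avoidable bias, not a flaw that undermines the trial.

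**What to change.** Reconcile section 17.1 with section 13. Replace the immediate-withdrawal clause with text along these lines: *they are recorded as having declined the intervention and researcher visits, remain in the trial, and are asked for the BDI-II alone by telephone at 4 and 12 months as in section 13, unless they refuse all further contact.*

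State in section 13 that the telephone request applies in the same way in both arms, whenever visits are declined and not only after a missed appointment. Record three things separately: refusal of the intervention, refusal of visits, and refusal of all contact. Loss to follow-up can then be reported by arm and by reason.

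The cost is one amended sentence with its cross-reference, one database status code and a few extra telephone calls by a route the protocol already has. The right to withdraw at any time is unchanged, and no sample size figure changes.

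### Section 17.1 ends outcome follow-up along with the dangerous contact when a participant indicates serious risk, and one of its three settings exists only in the intervention arm

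*Protocol*

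**What the plan says.** The rule is in Protocol section 17.1: "Participants will also be withdrawn from the trial if they indicate during assessment/qualitative/CAB appointments that on-going participation would be likely to result in". The consequence that this sentence then names is "serious risk of harm to the participant themselves or to members of the study team or CAB service". What is withdrawn from is the trial, and three settings are listed: assessment visits, qualitative interviews and CAB appointments.

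The surrounding text treats intervention and follow-up separately:

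- Section 17.1, the paragraph before the rule: "The trial analysis is based on intention to treat, so all participants will be encouraged to continue with follow-up as per protocol". This holds even when appointments are missed or the intervention is only partly delivered.
- Section 17: "Participants who withdraw from the intervention and/or follow-up will not be replaced within the study". Data gathered before withdrawal are kept unless the participant asks for their removal.

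On who has CAB contact, section 12.3 says "The case manager for participants in the intervention arm will usually be the CAB advisor". Section 12.1 gives controls GP care and leaflets, with no trial CAB contact.

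On keeping the outcome, section 13 provides remote modes: "In the event that a face to face follow-up visit cannot be arranged, telephone, postal or on-line data collection options will be offered". Participants who want no further follow-up are asked whether they would "complete the single primary outcome questionnaire (BDI-II) by telephone".

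On risk found by researchers, section 15 stops the visit of an actively suicidal participant and allows a return once the GP has been consulted, so that "further participation in the study has been assessed as appropriate by a clinical expert". For CAB contacts, section 15 refers only to CAB's own protocol and guidance.

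**The concern.** The trigger is narrow, but the consequence is wide. A participant may be a danger only in CAB meetings, for example through hostility to an advisor. As written, that participant leaves the whole trial, and the 12-month BDI-II is not requested even if a telephone call or a postal form would be safe.

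Two of the three listed settings occur in both arms: every participant has assessment visits, and qualitative sampling (section 16.2) is not restricted by arm. The third, trial CAB appointments, does not occur in the control arm. A post-randomisation rule that removes outcomes, and that has an extra point of entry in one arm, can create a difference in missing data linked to allocation. The intention-to-treat comparison at 12 months (section 21.2) is meant to avoid this. At stake are a few primary outcomes and a possible small bias of unknown sign.

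**Working it through.** **Text check.**

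| Question | Control arm | Intervention arm |
|---|---|---|
| Assessment visits, a listed setting | Yes | Yes |
| Qualitative interviews, a listed setting | Yes, if sampled | Yes, if sampled |
| Trial CAB appointments, a listed setting | No (12.1) | Yes (12.2, 12.3) |
| Pause and return for suicidality at a data collection visit (15) | Yes | Yes |
| Pause and return for risk disclosed at a CAB appointment | Not applicable | Not stated |
| Pause and return for risk to staff | Not stated | Not stated |
| Remote BDI-II extended to withdrawal under the harm rule (13) | Not stated | Not stated |

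Controls may attend CAB by other means (17.1). Those are not trial appointments, and no route is described by which they would trigger the rule.

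**Size.** The Protocol gives no rate for this trigger and no BDI difference between those who meet it and the rest. The arithmetic therefore shows only how much loss would be needed to matter.

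*Inputs from section 21.1:* difference 3.5, SD 9, two-sided 5%, 135 per arm for 90% power, 20% attrition, 195 per arm (individual randomisation) or 235 per arm (cluster).

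*The plan's own figure.* A two-sample normal calculation gives 139 per arm, and the t-test gives 139.9. The stated 135 is within 3% of these and has t-test power of 0.8895. The point does not depend on this gap.

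*Expected completers per arm:* 0.8 × 195 = 156; 0.8 × 235 = 188.

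*Shift in the intervention-arm mean* = (net extra losses ÷ completers) × gap. Here gap is the baseline-adjusted BDI difference between those lost and those kept, and its sign may be positive or negative. Gaps of 5, 10 and 15 points are assumed.

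| Assumed gap | Shift per net loss, 156 completers | Net losses for a 0.35 shift, 156 completers | Net losses for a 0.35 shift, 188 completers |
|---|---|---|---|
| 5 | 5/156 = 0.032 | 0.35 × 156/5 = 10.9, so 11 (7.1%) | 0.35 × 188/5 = 13.2, so 14 |
| 10 | 10/156 = 0.064 | 0.35 × 156/10 = 5.5, so 6 (3.8%) | 0.35 × 188/10 = 6.6, so 7 |
| 15 | 15/156 = 0.096 | 0.35 × 156/15 = 3.6, so 4 (2.6%) | 0.35 × 188/15 = 4.4, so 5 |

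The 0.35 is 10% of the 3.5-point target. As a second scale, an assumed net loss of 1% to 2% with a gap of one SD (9 points) shifts the mean by 0.01 × 9 = 0.09 to 0.02 × 9 = 0.18 units.

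*Power.* Four net losses among 156 completers are 4/156 = 2.6%. Applied to 135 in one arm this leaves 135 × (1 − 4/156) = 131.5. The t-test power with 135 v 131.5 is 0.8855, a fall of 0.4 percentage points from 0.8895.

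**The case against.** The strongest reply is that the sentence can be read narrowly. Its trigger is harm from staying in the trial, not harm from CAB contact. A participant who merely stops seeing CAB could fall under the preceding paragraph as having partly completed the intervention, and so stay in follow-up. This is a reasonable reading, but the text does not state it. The rule lists CAB appointments as a setting and the CAB service as a party at risk, and then withdraws the participant from the trial.

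A second reply is that safeguards exist. Section 15 covers suicidality, the most foreseeable risk here, with pause and return at data collection visits in both arms. It would be wrong to infer that the Protocol has no shared review of risk. What remains uncovered is risk disclosed at CAB appointments and risk to staff. CAB manuals and agreements are not shown and may add steps. Reasons for withdrawal go to the CTU, and repeated-measures and missing-data sensitivity analyses are planned (21.2). These help, but they do not recover an outcome that was never requested.

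A third reply is that an extra setting for disclosure is not the same as extra missing outcomes. The same person might trigger the rule at the 4- or 12-month visit in either arm, which would shrink the net difference towards zero. This stands, and it limits the claim.

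The last reply concerns the remedy: a review by the practice GP would give the decision to someone who knows the allocation (10.5, 11.1). This also stands, and the fix below avoids it.

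**Conclusion.** The point holds as a cheap improvement at the lowest severity. Section 17.1 joins two decisions that the rest of section 17 keeps apart, and it gives the intervention arm one extra setting for losing the 12-month BDI-II.

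The effect is probably small. Under the assumed gaps of 5 to 15 points, each net extra loss moves the arm mean by about 0.03 to 0.10 units. The 4 to 11 net losses needed for a 0.35 shift are more than a rare trigger is likely to produce. The effect on power is negligible.

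A reader might infer that the rule removes the most depressed participants from the intervention arm and so favours it. The Protocol does not support that: a participant who endangers staff need not have a high BDI, and no figures are given, so the direction is unknown. Nor does the text show that intention to treat is defeated. It shows an avoidable route to missing data. These sizes rest on 20% attrition, the stated sample sizes and assumed gaps. No trigger rate can be derived from the Protocol.

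**What to change.** Amend section 17.1 to say:

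- The contact that creates the risk (CAB contact, face-to-face research visits, or both) stops at once.
- The participant stays in outcome follow-up, and the 4- and 12-month BDI-II are requested by the telephone, postal or on-line modes of section 13 if the participant agrees.
- Full withdrawal applies where follow-up itself is judged to pose the risk. That judgement follows the same rule in both arms and is made, where possible, by a clinician not told the allocation. The local principal investigator is one candidate: section 15 describes these as senior clinicians, and their notifications under 11.1 omit the allocation. The practice GP, who knows it, should not decide.
- The outcome assessor is not told which contact was stopped, since that could reveal the arm (11.3).

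Where the danger is to CAB staff, the facts of the case may reveal the arm to the deciding clinician, hence the words where possible.

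The cost is a few sentences, a few extra clinician reviews and a few remote BDI-II requests. Immediate protection from the dangerous contact is kept.
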